**Use of oral pregabalina as preemptive analgesia in abdominal
hysterectomy: evaluation of postoperative pain in a
randomized clinical trial.**

Register Clinical Trials (clinicaltrials.gov): NCT04495374

January, 20, 2021

METHODS

Study design

This study is revealed to be an experimental, randomized, double-blind, controlled placebo controlled clinical trial. The trial included only female patients, who would undergo abdominal hysterectomy surgery under spinal anesthesia, where after randomization as patients they were allocated into two groups, the placebo controlled group (P0) and the pregabalin 300 mg group (P1).

The entire study had been carried out a research protocol in accordance with the recommendations of the Consolidated Standards of Reporting Trials (CONSORT). The revised CONSORT statement in 2010, consists of a list of 25 items in a table that configure a checklist with guidelines for the development of randomized clinical trials with parallel groups, this statement also contains a flowchart to guide the experimental design of the study.

Study location and period

All procedures, procedures and data collections for this study were carried out at Santa Casa de Alfenas - MG (Casa de Caridade Nossa Senhora do Perpétuo Socorro). The inclusion of patients in the study and the collection of data from September 2019 to September 2020.

Sample population

Initially the sample size was out of base from a pilot study carried out with 10 patients, where establishing a 95% confidence level and a power above 80% using non-parametric tests (Mann-Whitney test) for primary study outcomes, to decide to make an initial allocation of 51 patients in each study group, totaling 102 patients. These 10 patients in the pilot study were also included in the final version of the study.

Prepared to an atypical health scenario issued by the pandemic of COVID-19, during the year of 2020, in the month of September of that same year to choose to carry out new statistical analyzes with a population included so far in the study. From these new analyzes, the results obtained were statistic for the primary outcomes and due to difficulties imposed by the pandemic caused by the coronavirus, it was decided to interrupt the data collection at this time, totaling a total of 55 patients included in the study.

The inclusion criteria are detailed below, where all are mandatory, and also the criteria and exclusion used to define the sample population.

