Inclusion criteria: (1) Female patients; (2) Age between 20 and 65 years; (3) Patients who will undergo elective abdominal hysterectomy surgery due to benign pathologies; (4) Be classified as physical status by the Society of Anesthesiologists (ASA) as ASA I (healthy individual) or ASA II (patient with mild and controlled systemic disease);

Exclusion criteria: (1) Allergy or known intolerance to pregabalin or opioids; (2) Patients with chronic pain or fibromyalgia; (3) Patients on chronic use of opioids; (4) carriers of malignant neoplasms; (5) Pregnant women; (6) People with active uncontrolled cardiovascular disease; (7) Patients with kidney and / or liver disease; (8) Patients who have spinal deformities that make spinal anesthesia impossible; (9) Presence of coagulation disorders or anticoagulant therapy that cannot be suspended for surgery; (10) Presence of active sepsis;

After accepting to participate in the study and signing the informed consent form, the sociodemographic data of all patients were collected through a questionnaire, for further analysis.

Groups and interventions

As this is a randomized clinical trial, this study was made up of two groups. The group P0, the group designated as placebo controlled, and the group P1, consisted of patients participating in the intervention group.

Group P0: Received two placebo tablets composed of starch and aerosil (colloidal silicon dioxide).

Group P1: They received two tablets identical to the tablets in group P0, but in this case, the tablets were each composed of pregabalin in the 150mg dosage, totaling a total dosage of 300mg of pregabalin.

All tablets were made in the same pharmacy handling, under conditions provided for in good manufacturing practices, to avoid bias.

Blinding

In order to avoid measurement bias, after elaboration, the tablets were placed in opaque and sealed envelopes, being identified only as formula A or formula B. An external researcher, who was not involved in randomization or data collection, was responsible by blinding, being the only researcher to know the composition of each formula. At the end of the study, this researcher informed the rest of the team of the composition of each formula, with Formula A consisting of two tablets of 150 mg of pregabalin each, and Formula B consisting of two placebo tablets.

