Since the patients included in the study, the researcher responsible for medication randomization and administration, and also the researcher responsible for monitoring and collecting data, did not have knowledge about the composition of the interventions (formula A and formula B).

Randomization

After determining the sample population and preparing interventions in sealed and opaque envelopes, the randomization procedure had been carried out. To carry out the random allocation process, an external researcher was responsible for administering to the patient a sealed, opaque envelope containing the intervention (placebo or pregabalin 300mg) over a period of 02 hours prior to the start of the anesthetic-surgical procedure, with randomization it was simple, carried out by entering the study, where the first patient to be admitted to the study received formula A intervention, and the second received formula B, and so on. Another researcher was responsible for the patient's perioperative follow-up and data collection.

Experimental draw

A total of 58 patients were selected for the research. After randomization, 30 patients were allocated to the P0 group (placebo), but during the follow-up two were excluded, one due to the use of subarachnoid morphine and the other due to the use of analgesic medications (tramadol) in the immediate postoperative period, which was not included in the study protocol. In the P1 group (pregabalin 300mg), 28 patients were allocated, in which one patient had to be excluded due to the use of subarachnoid morphine during anesthesia. Thus, the analyzes were performed with a total of 28 patients in the P0 group and a total of 27 patients in the P1 group.

Evaluation procedures and measures

After the patient inclusion process, blinding and random allocation to groups were carried out. The patients participating in the P0 group received a sealed envelope containing two placebo tablets, while patients belonging to the P1 group received an identical envelope containing two tablets of 150mg pregabalin each, all tablets were administered within two hours prior to the start of surgery. , in the nursing room where the patients were hospitalized.

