At the end of the surgery, the patients were referred to the PACU, where they were monitored again, and went through the pain assessment process using the visual analog scale (VAS) in relation to pain at rest and “movement” (the patient was asked to perform the forced cough movement), through a direct question with scale demonstration. Pain characterized as mild (0 - 2 VAS) received no medication, in addition to those already prescribed; pain characterized as moderate (3 - 7 EVA) received IV morphine at a dosage of 0.025 mg.kg⁻¹; and severe pain (8 - 10 VAS) received IV morphine at a dosage of 0.05 mg.kg⁻¹ every 01 h until analgesic control. To be considered able to be discharged from the PACU for clinical follow-up in wards, patients should reach a score ≥ 9 on the modified Aldrete Scale (Table 3) and have VAS pain scores ≤ 2 .

Upon arriving at the infirmary, patients were periodically evaluated at regular intervals in relation to the intensity of pain, with the help of a team of properly trained and qualified nurses. For patients who presented moderate-intensity pain (VAS $\geq 2 < 8$) or pain classified as severe (VAS ≥ 8), IV morphine was administered at a dose of 1 mg and 2 mg, respectively, according to a medical prescription. All analgesic medications used were recorded in the patient's medical record. 24 h after discharge from the PACU, in the ward, the patient was evaluated by the same examiner who performed the evaluation in the PACU, who again performed the stratification of pain by VAS and an evaluation with the McGill questionnaire.

During the entire hospitalization period of the study patients, the use of CNS depressant drugs (example: ketamine, droperidol, promethazine) and / or analgesic drugs that are not included in the study protocol was avoided. If any of the patients were medicated with such drugs, they would be excluded from the study to avoid bias in the statistical analysis. The data related to surgery (pre, trans and postoperative) were collected for statistical analysis, according to Annex II, in which, for example, the total duration of surgery in minutes was described; the total of intravenous fluids infused; the values of mean arterial pressure and heart rate in the pre, intra and postoperative period;

the presence or not, as well as the quantity, of PONV in the PACU and after 24h; presence or not of dizziness as a possible side effect, among others.

Outcomes

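### Three of 58 allocated patients are dropped for non-protocol drugs given after dosing, one of them for postoperative tramadol on placebo, and no as-allocated analysis is described

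*Combined protocol and SAP*

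**What the plan says.** The rule is in the section Evaluation procedures and measures. It covers the whole hospital stay and any CNS depressant or analgesic outside the protocol: "If any of the patients were medicated with such drugs, they would be excluded from the study to avoid bias in the statistical analysis".

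The section Experimental draw shows it applied. Of 58 patients, 30 were allocated to placebo and "during the follow-up two were excluded": one for subarachnoid morphine, "the other due to the use of analgesic medications (tramadol) in the immediate postoperative period". Of the 28 allocated to pregabalin, "one patient had to be excluded due to the use of subarachnoid morphine during anesthesia". As a result, "the analyzes were performed with a total of 28 patients in the P0 group and a total of 27 patients in the P1 group". The tablets were taken before surgery, so all three exclusions came after allocation and dosing.

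The section Sample population gives the trial's size as "totaling a total of 55 patients included in the study", without the 58.

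Under Outcomes, pain on the VAS and McGill scales is primary. Total postoperative opioid dose and time to first analgesic rescue are secondary. The section Statistical analysis lists tests, software and the 5% level. It defines no analysis population, no sensitivity analysis and no handling of data recorded after a non-protocol drug.

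**The concern.** Removing patients because of something that happened after allocation does not protect a comparison from bias, and it can introduce bias if the event is related to outcome. The tramadol patient is the clear case. Extra analgesia soon after surgery is the kind of event that the secondary outcome is meant to count, and it may also reflect the pain that the primary outcome measures. Under the rule, the patient and the event both leave the data.

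The two subarachnoid-morphine exclusions are less tied to outcome. There is one per arm, and the route is spinal, not postoperative rescue. They still followed dosing.

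What is at stake is whether a result close to 0.05 depends on these three patients. With only the 55-patient analysis described, a reader cannot tell.

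**Working it through.** **1. Counts (Experimental draw).** 30 − 2 = 28; 28 − 1 = 27; 28 + 27 = 55; 58 − 55 = 3. The plan's figure of 55 is reproduced exactly.

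**2. Size and balance.** 3/58 = 5.2% removed; 2/30 = 6.7% on placebo and 1/28 = 3.6% on pregabalin; Fisher's exact p = 1.0. One exclusion of 58 (1.7%) is an outcome-type event.

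**3. Any postoperative opioid use.** Assumption: tramadol counts as an opioid (the document calls it only an analgesic). If x of the 28 analysed placebo patients used an opioid, restoring this patient moves the share from x/28 to (x + 1)/29. For x = 0 that is +3.4 points, for x = 14 +1.7 points, and for x = 28 no change.

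**4. Bounds for the Mann-Whitney test.** The documents give no p-values, so the 55-patient p is assumed (two-sided, no ties). U has mean n₁n₂/2 and SD √(n₁n₂(n₁ + n₂ + 1)/12).

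- 28 v 27: mean 378, SD 59.40. For p = 0.05, U = 378 + 1.96 × 59.40 = 494.4.
- 30 v 28: mean 420, SD 64.27. The new between-group pairs number 840 − 756 = 84.
- All 84 against pregabalin: z = (494.4 − 420)/64.27 = 1.16, p = 0.247.
- All 84 for pregabalin: z = (494.4 + 84 − 420)/64.27 = 2.47, p = 0.014.
- Split evenly (42): z = 1.81, p = 0.070.

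| Assumed 55-patient p | All three restored | Tramadol patient only (29 v 27) |
|---|---|---|
| 0.05 | 0.014 to 0.247 | 0.033 to 0.092 |
| 0.01 | 0.002 to 0.084 | 0.006 to 0.022 |
| 0.001 | 0.0002 to 0.017 | 0.0006 to 0.0029 |

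**5. Simulated VAS.** Assumptions: scores rounded to 0–10, SD 2.2, means 4.2 v 3.0, 28 v 27, 1000 datasets per band of 55-patient p. Worst is VAS 10 and best is VAS 0. Entries are median p over datasets. Ranges in rows 2 and 3 span the two morphine patients both best, both at the pooled median, or both worst.

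| Placement of the restored patients | Band 0.03–0.05 | Band 0.01–0.03 | Band 0.001–0.01 |
|---|---|---|---|
| None restored | 0.039 | 0.018 | 0.004 |
| Tramadol worst, morphine patients alike | 0.026–0.035 | 0.012–0.017 | 0.003–0.004 |
| Tramadol best, morphine patients alike | 0.069–0.088 | 0.035–0.048 | 0.009–0.014 |
| Both placebo worst, pregabalin best | 0.011 | 0.005 | 0.001 |
| Both placebo best, pregabalin worst | 0.191 | 0.115 | 0.040 |

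These are medians, not limits. In the 0.03–0.05 band single datasets run from about 0.008 to 0.25. In the 0.001–0.01 band they reach about 0.08, and only the last row crosses 0.05, in about a third of datasets.

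Neutral case: with all three at the pooled median, the 0.03–0.05 band keeps a median near 0.04, and about 7% of datasets exceed 0.05. This is milder than the even split in step 4, because a placebo patient at the pooled median still lies above more than half of a lower-scoring pregabalin group.

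**6. Simulated opioid dose, tramadol patient alone restored.** Assumptions: zero dose in 30% v 50%, otherwise 1 + Poisson(2.0) v 1 + Poisson(1.5). In the 0.03–0.05 band the baseline median is 0.039. It becomes 0.025 if tramadol is the highest dose and about 0.042 if it is the lowest non-zero dose. In the second case p rises in about 75–80% of datasets across the three bands.

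**The case against.** The strongest reply is that the matter is small and open. The rule is stated. Experimental draw gives the 58, both allocations, all three reasons and the 28 v 27. Exclusions are nearly balanced. The researchers giving the tablets and collecting data did not know the formulas, and "At the end of the study, this researcher informed the rest of the team of the composition of each formula". Restoring the three at the pooled median changes little. With the morphine patients treated alike, every simulated crossing of 0.05 in step 5 needs the tramadol patient at VAS 0. The other crossings need the two morphine patients at opposite extremes. Restoring the morphine patients also brings in a spinal opioid that the plan did not intend, which is a choice of estimand. All of this stands, and it limits the point to a modest one. It does not justify the rule, and disclosing the exclusions does not show their effect.

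A reader might infer more in three ways, and the documents support none of them.

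- **That the direction is known.** It is tempting to say that dropping a placebo patient who needed tramadol works against pregabalin. The reason for the tramadol is not given. Even if it was for pain, the patient could rank low on total opioid dose (step 6), and the 24 h VAS and McGill scores come after the drug.
- **That exclusions were made with knowledge of the arm.** The text does not say who decided them, but it describes blinded staff and unblinding at the end.
- **That the result would change.** This is a methods text without results. It can be faulted for describing no as-allocated analysis, not for a finding that fails.

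**Conclusion.** The point holds and should be fixed, at modest weight. An exclusion rule based on events after dosing is justified as avoiding bias, yet it deletes a placebo patient for an event of the secondary-outcome kind, and no analysis of the allocated groups is described. The direction is unknown: restoring the tramadol patient strengthens the pregabalin comparison if she ranks worst, and can weaken it if she ranks low on pain or opioid dose.

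The counts are exact. Every p-value above except Fisher's rests on assumed data. On those assumptions the three patients could decide a 55-patient result near 0.05. They would rarely matter for one between 0.001 and 0.01, where only the single most adverse placement crosses 0.05. Treating tramadol as an opioid is also an assumption.

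**What to change.** - Report an analysis of all 58 patients in their allocated groups (30 v 28), labelled post hoc, beside the 28 v 27 analysis labelled per-protocol.
- Count tramadol in postoperative opioid use, with a conversion factor stated and fixed before the re-run (the documents give none). Count it as a first-rescue event if the record shows it was given for pain.
- Where scores do not exist or the reason for tramadol is not recorded, give best-rank and worst-rank bounds and the neutral case. Place the two morphine patients both alike and at opposite extremes.
- In Sample population, replace the statement that 55 were included with 58 allocated and 55 analysed, to match Experimental draw.

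The cost is a wording change, a review of three medical records (the plan says analgesics used were recorded there) and one re-run.

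There are downsides. Three protocol deviations enter the estimate. The 24 h VAS and McGill scores may not exist for excluded patients, leaving only bounds. The analysis comes after collection and unblinding. It also cannot repair the allocation method: Randomization says that "the first patient to be admitted to the study received formula A intervention, and the second received formula B, and so on", which is alternation, and strict alternation would give 29 v 29, not 30 v 28. That is a separate issue.

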In the operating room, venoclysis was performed with jelco No. 18 or No. 20, and an infusion of 08 ml.kg-1 of crystalloid solution (lactated ringer). The patients were properly monitored with pulse oximetry, cardioscope, and non-invasive blood pressure monitor. After monitoring, patients were premedicated with intravenous (IV) midazolam at a dosage of 0.03 mg.kg-1

To perform spinal anesthesia, the patients were seated on the surgical stretcher by the nursing team. Asepsis and antisepsis were performed at the puncture site with alcoholic chlorhexidine solution. After placement of sterile drapes, local anesthesia was performed with 2.0% lidocaine without vasoconstrictor. The first attempt at subarachnoid puncture was performed, using the median technique, between the intervertebral levels L3-L4 or L4-L5 or L5-S1, with a 25G Quincke needle for subarachnoid anesthesia. In case of technical difficulty in the puncture, the paramedian puncture technique was chosen. The confirmation of the correct puncture was based on the aspiration of cerebrospinal fluid. Anesthesia was performed with the local anesthetic 0.5% bupivacaine at a dosage of 0.3 mg.kg-1, injected from a 5 ml disposable syringe. After anesthesia, the patients were placed in the supine position, and the correct level of anesthesia was proven with thermal sensitivity tests using cotton soaked with alcoholic solution. After the anesthesia reached the sensory level of the T4 thoracic vertebra, the surgical team was allowed to start the procedure. Prior to the beginning of the surgical incision, a delayed bladder probe was performed in all patients according to the surgeon's indication. All surgeries were performed by the same team of surgeons.

Hemodynamic changes in blood pressure were controlled with the use of vasoactive medications such as ephedrine or metaraminol. For prophylaxis of postoperative nausea and vomiting (PONV) ondansetron was administered at a dosage of 4 mg intravenously (IV) 30 minutes before the end of surgery. It was prescribed for all

tenoxicam patients at a dosage of 20 mg IV at regular intervals every 12 hours for the purpose of anti-inflammatory and analgesic action. For analgesic relief, dipyrone IV was also prescribed at a dosage of 50 mg.kg⁻¹ at regular intervals every 6 hours. During the surgery, and also at the end of the surgery, the patients were evaluated for the degree of sedation using the Ramsay sedation scale as a basis.

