The primary outcome was the assessment of postoperative pain using two different scales, the traditional visual analog scale (VAS) and the McGill Pain Questionnaire. The secondary outcome was the comparative analysis between the groups of opioid consumption in the postoperative period, evaluating both the total dosage of opioids used, as well as the time between the end of surgery and the request for the first analgesic rescue dose.

Other outcomes that were analyzed, apart from the variation in patients' hemodynamic data during the surgical times (pre, intra and immediate postoperative period), the degree of sedation was also evaluated using the Ramsay scale, and the presence of side effects such as nausea and vomiting, itching and dizziness. Other independent variables were analyzed, such as age, weight, body mass index, education level, profession, family income.

Ethical aspects and records

This study with the objective of preserving the patients' physical and psychological integrity followed the statements enunciated by the Declaration of Helsinki. All patients previously admitted to the study were clarified about the methodological process, the randomization and blinding process, the guarantee of confidentiality, about possible side effects of the interventions and also about the risks and benefits of participating in the study and the consent costs for participation in it. After clarifying any doubts and consenting to the patients' participation, the free and informed consent form (ICF) was signed, to which one of the copies was delivered to the patient and another copy was filed with the study researchers.

According to Resolution No. 466 of December 12, 2012, of the National Health Council, which addresses the guidelines and regulatory standards for research involving human beings, this study was approved by the Research Ethics Committee (CEP) of UNIFAL- MG under opinion number 3,334,050 on June 17, 2019 (ANNEX IV). This research was also recorded in the North American database for the registration of clinical trials, Clinical Trials (clinicaltrials.gov), under the protocol NCT04495374.

Statistical analysis

Descriptive analysis (median, mean and standard deviation) was performed for continuous variables that followed a standard distribution, and these were expressed in a table.

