When analyzing parametric variables, the t test was used, and in comparisons between groups, the t test was used for independent samples, and in the analysis of data at different points in time between patients in the same group, we chose to use the test. t paired.

When evaluating non-parametric variables, the Mann-Whitney test was chosen. To compare numerical measurements between the times in each group, the Wilcoxon test was used for the related samples. To assess qualitative variables, Pearson's chi-square test or Fisher's exact test was chosen.

All data obtained were digitized and analyzed using the Statistic® 7.0 software, with a significance level of 5% ($p < 0.05$). For the elaboration of statistical graphs, the program used was the GraphPad Prism version 5.00 (Trial) of 2007.

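### Time to first rescue is analysed with t test or Mann-Whitney only, with no method or rule for patients who never needed rescue

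*Combined protocol and SAP*

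**What the plan says.** The Outcomes section gives the secondary outcome two components: total opioid dose and "the time between the end of surgery and the request for the first analgesic rescue dose".

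The Statistical analysis section states that "in comparisons between groups, the t test was used for independent samples" for parametric variables, and that "When evaluating non-parametric variables, the Mann-Whitney test was chosen". Its other tests do not apply here: paired t and Wilcoxon are within-group, and chi-square and Fisher are for qualitative data. It names no Kaplan-Meier, log-rank or Cox method and does not say which test applies to this outcome.

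Evaluation procedures and measures makes rescue depend on pain. In the PACU, "Pain characterized as mild (0 - 2 VAS) received no medication" beyond what was already prescribed, so morphine starts at VAS 3. On the ward it starts at VAS 2. Background analgesia was scheduled: "tenoxicam patients at a dosage of 20 mg IV at regular intervals every 12 hours", and "dipyrone IV was also prescribed at a dosage of 50" mg/kg every 6 hours. The last assessment is timed from PACU discharge, not from the end of surgery: "24 h after discharge from the PACU, in the ward, the patient was evaluated by the same examiner". That time point is given for the VAS and McGill evaluation and is not linked to the rescue outcome.

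**The concern.** A patient who never reaches the morphine threshold has no first-rescue time. All that is known is that it exceeds the observation period, so it is censored. Neither stated test can use such a patient until someone decides what to do with her: leave her out, rank her as tied longest, or assign a time. The plan does not say which.

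The choice matters because never-rescued patients are the ones with the best pain control. If pregabalin works, they should be more frequent in the pregabalin arm, and leaving them out removes the patients who benefited most. The comparison is then between groups selected by outcome, and the estimated difference shrinks. Assigning zero would be worse, since it treats the best outcome as the worst. A reader of the results could not tell which was done.

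**Working it through.** **The plan's own figure.** None is given for this outcome. The 51 per group in Sample population refers to the primary outcomes, and it cannot be reproduced because no effect size or SD is stated. Nothing below depends on it.

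**Inputs from the document.** 28 placebo and 27 pregabalin patients analysed (Experimental draw); 5% significance level (Statistical analysis).

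**Assumptions.** The documents give no rescue rates. Assumed: two-sided testing, exponential times from the end of surgery, a 24 h cut-off, and hazard ratio (HR) 0.50 for the main table.

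**Formulas.** With proportion *p* rescued by 24 h:
- Rate = -ln(1 - p)/24.
- Under HR 0.50, 1 - p1 = (1 - p0)^0.5. For p0 = 0.98, the square root of 0.02 is 0.141, so p1 = 0.859.
- Expected never rescued = 28(1 - p0) + 27(1 - p1). For 0.98 v 0.859: 28 × 0.02 + 27 × 0.141 = 0.56 + 3.81 = 4.4.

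**Power.** 10,000 simulated trials per row, Monte Carlo standard error at most 0.5 points:

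| Rescued by 24 h, placebo v pregabalin | Expected never rescued of 55 | Mann-Whitney, dropped | Mann-Whitney, tied longest | Loss (points) | Log-rank |
|---|---|---|---|---|---|
| 99.99% v 99.0% | 0.3 | 0.565 | 0.586 | 2 | 0.705 |
| 99.9% v 96.8% | 0.9 | 0.521 | 0.584 | 6 | 0.705 |
| 99.5% v 92.9% | 2.1 | 0.448 | 0.585 | 14 | 0.705 |
| 99% v 90.0% | 3.0 | 0.395 | 0.575 | 18 | 0.690 |
| 98% v 85.9% | 4.4 | 0.331 | 0.570 | 24 | 0.678 |
| 95% v 77.6% | 7.4 | 0.231 | 0.575 | 34 | 0.670 |

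For the t test, dropping these patients rather than assigning them 24 h costs 3, 9, 17, 22, 28 and 38 points in the same order.

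**Estimate.** True median = ln 2/rate; rescued-only median = -ln(1 - p/2)/rate. At 98% v 85.9% the rates are 0.163 and 0.0815 per hour. The true medians are 4.3 and 8.5 h and the rescued-only medians 4.1 and 6.9 h, so the difference falls from 4.2 to 2.8 h.

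**Heavier non-rescue.** These rows use stronger effects and are not comparable with the table. At 90% v 60% (HR 0.40), 80% v 50% (HR 0.43) and 70% v 40% (HR 0.42), with 13.6, 19.1 and 24.6 never rescued, Mann-Whitney power is 0.20, 0.11 and 0.07 if dropped, against 0.78, 0.65 and 0.61 if tied.

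**Coding as zero.** In the same three scenarios, Mann-Whitney was significant in the wrong direction in about 23%, 36% and 42% of simulated trials. At 98% v 86% this happened in under 1%.

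**No true effect.** At 80%, 95% and 99% rescued in both arms, rejection was 4.6% to 5.6% for the dropped, tied or 24 h-assigned analyses and log-rank. Zero coding gave 4.4% to 5.0% in a smaller run (4,000 trials; 60%, 80% and 95% rescued).

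**The case against.** The strongest reply is that the harm needs two facts the documents do not supply: that some patients were never rescued, and that they were mishandled. On the first, the ward rule gives morphine from VAS 2, with periodic checks by trained nurses, after open abdominal surgery. Patients given subarachnoid morphine were excluded. A patient had to stay below 2 at every ward check to escape rescue, which points to high rescue rates and the smaller losses in the table. On the second, Experimental draw says the analyses used 28 and 27 patients, which leans towards everyone being kept. If they were ranked as tied longest, Mann-Whitney is a valid test.

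Much of this stands. The scenarios with 14 or more never-rescued patients have no support in the text. The log-rank advantage over tied Mann-Whitney in the table, about 10 to 12 points, is also no measure of mishandled censoring. It is as large where almost nobody is censored, because exponential times with proportional hazards favour log-rank, and log-rank ran at 5.2% to 5.6% under the null. The constant hazard ignores the spinal block and the periodic timing of checks. The unstated cut-off is minor too: it matters only for first rescues between 24 h after surgery and the later 24 h assessment.

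The gap itself remains. The 28 and 27 describe the analysis set, not the value given to a patient without an event. Two or three such patients dropped out of 55 would still cost 14 to 18 points.

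**Conclusion.** The concern holds as a gap of minor to moderate severity that is cheap to close. A time-to-event component of the secondary outcome has no censoring method and no stated handling of never-rescued patients. The size depends on an unreported count: no effect if it is zero, and if such patients were dropped, the losses tabulated above under exponential times, HR 0.50 and a 24 h cut-off.

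A reader might infer more than the text supports:
- *That patients were dropped.* Nothing says so.
- *That Mann-Whitney is wrong here.* It is valid if never-rescued patients are ranked as tied longest at a common cut-off.
- *That a significant result would be a chance finding.* With no true effect, every handling examined stays near 5%.
- *Conversely, that the only risk is a missed effect.* Zero coding can give significance in the wrong direction when a real effect exists and many patients are unrescued.
- *That the trial's main conclusion is at risk.* The primary VAS and McGill comparisons are not touched.

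**What to change.** Report the number never rescued in each arm. If it is zero, the stated tests suffice and nothing else is needed.

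Otherwise, analyse all 28 and 27 patients by Kaplan-Meier and log-rank, with a Cox hazard ratio and 95% CI. Censor never-rescued patients at their own 24 h assessment or, if the PACU discharge time was not recorded, at 24 h after the end of surgery. If Mann-Whitney is kept, state that these patients are ranked as tied longest at one common cut-off.

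The cost is one count per arm and one re-run. No new data should be needed: first-rescue time is already an outcome, and "All analgesic medications used were recorded in the" patient's medical record. The downsides are that the re-run is post hoc on a secondary outcome, because data collection has ended, and should be labelled so, and that the hazard ratio assumes proportional hazards.
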